## 7.3 LOST TO FOLLOW-UP

A participant will be considered lost to follow-up if he or she fails to return for the follow up visit scheduled visit and study staff are unable to contact the participant after at least 3 attempts.

The following actions must be taken if a participant fails to return to the clinic for a required study visit:

- The site will attempt to contact the participant, reschedule the missed visit within 1 month, counsel the participant on the importance of maintaining the assigned visit schedule and ascertain if the participant wishes to and/or should continue in the study
- Before a participant is deemed lost to follow-up, the investigator or designee will make every effort to regain contact with the participant (where possible, 3 telephone calls, emails and text messages and, if necessary, a certified letter to the participant's last known mailing address or local equivalent methods). These contact attempts will be documented in the participant's medical record or study file.
- Should the participant continue to be unreachable, he or she will be considered to have withdrawn from the study with a primary reason of lost to follow-up]

## 8 STUDY ASSESSMENTS AND PROCEDURES

## 8.1 ENDPOINT AND OTHER NON-SAFETY ASSESSMENTS

**Evaluation of the intervention's impact on the primary study outcome, participants' weights:** We hypothesize that the TEEN HEED intervention will result in maintenance or decrease in BMI percentile. We chose this outcome because weight loss is consistently shown as the most powerful and effective diabetes prevention strategy.

Evaluation of the effectiveness of the TEEN HEED intervention on behaviors and mediators related to weight loss and diabetes prevention: We hypothesize that the intervention will lead to observable changes to diet, physical activity and weight control behaviors and that these and other mediators explain weight loss. We will assess whether the intervention leads to improvements in diet and physical activity behaviors and related mediators such as knowledge, attitudes, beliefs, self-efficacy, and social influences, and improvements in other measures of diabetes risk (such as HbA1c). Hypotheses will be tested by comparing changes in outcomes between baseline post-intervention follow-up. We will also conduct exploratory analyses to begin to understand whether any of these factors appear closely linked to pre-diabetes diagnosis or weight loss.

## 8.2 SAFETY ASSESSMENTS

We will adhere to the minimum DSMP standards of the PPHS as this study does not involve more than minimal risk to subjects.

## 8.3 ADVERSE EVENTS AND SERIOUS ADVERSE EVENTS

### 8.3.1 DEFINITION OF ADVERSE EVENTS

This protocol uses the definition of adverse event from 21 CFR 312.32 (a): any untoward medical occurrence associated with the use of an intervention in humans, ***whether or not considered intervention-related.***

### 8.3.2 DEFINITION OF SERIOUS ADVERSE EVENTS

### 8.3.3 CLASSIFICATION OF AN ADVERSE EVENT

#### 8.3.3.1 SEVERITY OF EVENT

For adverse events (AEs) not included in the protocol defined grading system, the following guidelines will be used to describe severity.

- **Mild** – Events require minimal or no treatment and do not interfere with the participant's daily activities.
- **Moderate** – Events result in a low level of inconvenience or concern with the therapeutic measures. Moderate events may cause some interference with functioning.

- **Severe** – Events interrupt a participant’s usual daily activity and may require systemic drug therapy or other treatment. Severe events are usually potentially life-threatening or incapacitating. Of note, the term “severe” does not necessarily equate to “serious”.]

### 8.3.3.2 RELATIONSHIP TO STUDY INTERVENTION/EXPERIMENTAL MANIPULATION

All adverse events (AEs) will have their relationship to study procedures, including the intervention, assessed by an appropriately-trained clinician based on temporal relationship and his/her clinical judgment. The degree of certainty about causality will be graded using the categories below.

- **Related** – The AE is known to occur with the study procedures, there is a reasonable possibility that the study procedures caused the AE, or there is a temporal relationship between the study procedures and the event. Reasonable possibility means that there is evidence to suggest a causal relationship between the study procedures and the AE.
- **Not Related** – There is not a reasonable possibility that the study procedures caused the event, there is no temporal relationship between the study procedures and event onset, or an alternate etiology has been established.

### 8.3.3.3 EXPECTEDNESS

A clinician with appropriate expertise in pre-diabetes will be responsible for determining whether an adverse event (AE) is expected or unexpected. An AE will be considered unexpected if the nature, severity, or frequency of the event is not consistent with the risk information previously described for the study procedures.

## 8.3.4 TIME PERIOD AND FREQUENCY FOR EVENT ASSESSMENT AND FOLLOW-UP

The occurrence of an adverse event (AE) or serious adverse event (SAE) may come to the attention of study personnel during study visits and interviews of a study participant presenting for medical care, or upon review by a study monitor.

All AEs, not otherwise precluded per the protocol, will be captured on the appropriate case report form (CRF). Information to be collected includes event description, time of onset, clinician’s assessment of severity, relationship to study procedures (assessed only by those with the training and authority to make a diagnosis), and time of resolution/stabilization of the event. All AEs occurring while on study will be documented appropriately regardless of relationship. All AEs will be followed to adequate resolution.

Any medical or psychiatric condition that is present at the time that the participant is screened will be considered as baseline and not reported as an AE. However, if the study participant’s condition deteriorates at any time during the study, it will be recorded as an AE.

Changes in the severity of an AE will be documented to allow an assessment of the duration of the event at each level of severity to be performed. Documentation of onset and duration of each episode will be maintained for AEs characterized as intermittent.

<Insert role or name> will record events with start dates occurring any time after informed consent is obtained until 7 (for non-serious AEs) or 30 days (for SAEs) after the last day of study participation. At each study visit, the investigator will inquire about the occurrence of AE/SAEs since the last visit. Events will be followed for outcome information until resolution or stabilization.

---

### 8.3.5 ADVERSE EVENT REPORTING

---

#### 8.3.6 SERIOUS ADVERSE EVENT REPORTING

N/A

---

#### 8.3.7 REPORTING EVENTS TO PARTICIPANTS

N/A

---

#### 8.3.8 EVENTS OF SPECIAL INTEREST

N/A

---

#### 8.3.9 REPORTING OF PREGNANCY

N/A

---

### 8.4 UNANTICIPATED PROBLEMS

---

#### 8.4.1 DEFINITION OF UNANTICIPATED PROBLEMS

This protocol uses the definition of Unanticipated Problems as defined by the Office for Human Research Protections (OHRP). OHRP considers unanticipated problems involving risks to participants or others to include, in general, any incident, experience, or outcome that meets all of the following criteria:

- Unexpected in terms of nature, severity, or frequency given (a) the research procedures that are described in the protocol-related documents, such as the Institutional Review Board (IRB)-approved research protocol and informed consent document; and (b) the characteristics of the participant population being studied;
- Related or possibly related to participation in the research (“possibly related” means there is a reasonable possibility that the incident, experience, or outcome may have been caused by the procedures involved in the research); and
- Suggests that the research places participants or others at a greater risk of harm (including physical, psychological, economic, or social harm) than was previously known or recognized.

---

#### 8.4.2 UNANTICIPATED PROBLEMS REPORTING

The investigator will report unanticipated problems (UPs) to the reviewing Institutional Review Board (IRB) and to the Data Coordinating Center (DCC)/lead principal investigator (PI). The UP report will include the following information:

- Protocol identifying information: protocol title and number, PI's name, and the IRB project number
- A detailed description of the event, incident, experience, or outcome
- An explanation of the basis for determining that the event, incident, experience, or outcome represents an UP
- A description of any changes to the protocol or other corrective actions that have been taken or are proposed in response to the UP

To satisfy the requirement for prompt reporting, UPs will be reported using the following timeline:

- UPs that are serious adverse events (SAEs) will be reported to the IRB and to the DCC/study sponsor/funding agency within <insert timeline in accordance with policy> of the investigator becoming aware of the event
- Any other UP will be reported to the IRB and to the DCC/study sponsor/funding agency within <insert timeline in accordance with policy> of the investigator becoming aware of the problem
- All UPs should be reported to appropriate institutional officials (as required by an institution's written reporting procedures), the supporting agency head (or designee), and the Office for Human Research Protections (OHRP) within <insert timeline in accordance with policy> of the IRB's receipt of the report of the problem from the investigator

---

#### 8.4.3 REPORTING UNANTICIPATED PROBLEMS TO PARTICIPANTS

N/A

## 9 STATISTICAL CONSIDERATIONS

### 9.1 STATISTICAL HYPOTHESES

**Evaluation of the intervention's impact on the primary study outcome, participants' weights:** We hypothesize that the TEEN HEED intervention will result in maintenance or decrease in BMI percentile. We chose this outcome because weight loss is consistently shown as the most powerful and effective diabetes prevention strategy.

Evaluation of the effectiveness of the TEEN HEED intervention on behaviors and mediators related to weight loss and diabetes prevention: We hypothesize that the intervention will lead to observable changes to diet, physical activity and weight control behaviors and that these and other mediators explain weight loss. We will assess whether the intervention leads to improvements in diet and physical activity behaviors and related mediators such as knowledge, attitudes, beliefs, self-efficacy, and social influences, and improvements in other measures of diabetes risk (such as HbA1c). Hypotheses will be tested by comparing changes in outcomes between baseline and post-intervention follow-up. We will also conduct

exploratory analyses to begin to understand whether any of these factors appear closely linked to pre-diabetes diagnosis or weight loss.

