**Endpoints\*:**

**Evaluation of the intervention's impact on the primary study outcome, participants' weights:** We hypothesize that the TEEN HEED intervention will result in maintenance or decrease in BMI percentile.

Evaluation of the effectiveness of the TEEN HEED intervention on behaviors and mediators related to weight loss and diabetes prevention: We hypothesize that the intervention will lead to observable changes to diet, physical activity and weight control behaviors and that these and other mediators explain weight loss.

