## 2 INTRODUCTION

### 2.1 STUDY RATIONALE

The number of youth with type 2 diabetes in the U.S. is projected to increase by 49 percent by 2050, with higher rates among minority youth. The Diabetes Prevention Program (DPP) is recognized as a sentinel study demonstrating the effectiveness of lifestyle interventions for diabetes prevention among pre-diabetic adults but has not yet been replicated in youth. In addition, such intensive interventions are often not sustainable in high risk communities with limited resources. One strategy that has been successfully employed in adults from such communities is peer based health education. Research suggests that like adults, young people are more likely to hear and personalize messages, and thus to change their attitudes and behaviors, if they believe the messenger is similar to them and faces the same concerns and pressures. However, there have been no peer led interventions in ethnic minority teens and no interventions focused specifically on weight loss for diabetes prevention. Finally, another challenge identified in existing youth health intervention programs is keeping youth engaged to enhance program participation and impact. One potential strategy is the use of mobile technologies (text messaging, mobile applications, social media) to support weight management programs, but to date use of such technologies has not been studied in youth. This study's overall objective is to use community-based participatory research (CBPR) to develop and pilot test a youth peer-led diabetes prevention intervention incorporating novel mobile health technologies for at-risk adolescents in a vulnerable New York City community. The central hypothesis is that such an intervention will lead to maintenance or decrease in BMI, improved dietary, physical activity and weight control behaviors, and decrease in diabetes risk.

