### 2.3.2 KNOWN POTENTIAL BENEFITS

### 2.3.3 ASSESSMENT OF POTENTIAL RISKS AND BENEFITS

## 3 OBJECTIVES AND ENDPOINTS

OBJECTIVES	ENDPOINTS
Primary	
Use an iterative process between academic and community partners to adapt and modify the pilot TEEN HEED intervention	1) maintain/reduce body mass index (BMI)
Use qualitative methods to evaluate strategies for using peer educators and novel mobile health technologies as part of a group lifestyle change program for diabetes prevention among at-risk ethnic minority youth	2) improve adolescent dietary, physical activity and weight control behaviors, and
Use community-based participatory research strategies to refine, test, and evaluate outcomes of a peer education diabetes prevention program for pre-diabetic ethnic minority adolescents.	3) improve other measures of diabetes risk. We are collecting data at baseline and post intervention. We are also obtaining additional qualitative data and examining feasibility and acceptability for a text messaging program to support teens as they make lifestyle changes.

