## 9.2 SAMPLE SIZE DETERMINATION

## 9.3 POPULATIONS FOR ANALYSES

## 9.4 STATISTICAL ANALYSES

### 9.4.1 GENERAL APPROACH

We will use descriptive statistics to summarize the variables. Analyses will primarily test the hypothesis that intervention participants will have maintenance/reduction of BMI. Secondary analyses will assess whether the intervention leads to improvements in diet and physical activity behaviors and related mediators such as knowledge, attitudes, beliefs, self-efficacy, and social influences. Hypotheses will be tested by comparing changes in outcomes between baseline and follow up. Initial bivariate comparisons will use t tests to compare continuous endpoints and the Wilcoxon matched pairs signed-rank test to compare ordinal endpoints. We will then conduct multivariable analyses (using logistic regression, general linear models, and mixed models) to adjust for potential confounders (such as age, race/ethnicity, gender, SES, and baseline BMI) and to account for the repeated observations per participant. Analyses will include the baseline level of each endpoint as a covariate and a continuous variable for time. Confidence intervals will be constructed around each parameter estimate of the intervention. We will estimate effect sizes for each measure using correction for small sample bias.

To monitor the community-academic partnership, we will track activities such as the communication between community-academic partners, number of participants at CAB meetings, number of manuscripts and presentations by academic-community partners, and policy-related outcomes. We will also ask CAB members to complete annual surveys to gauge how closely the research project aligns with principles of CBPR, including factors they may feel less comfortable discussing in a group, such as level of inclusion and trust.

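### The primary result is not fixed: current sections contradict each other on the variable, the visit and the contrast, and 9.4.2 is empty

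*Combined protocol and SAP*

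**What the plan says.** All references are to the combined protocol and SAP.

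**Variable.** Section 9.1 states "We hypothesize that the TEEN HEED intervention will result in maintenance or decrease in BMI percentile", under a lead-in that calls the primary outcome participants' weights. The same hypothesis stands in 8.1 and 9.4.7, and the synopsis endpoints (1.1) have "maintenance or decrease in BMI percentile". Elsewhere the variable is BMI: 2.1 expects that "such an intervention will lead to maintenance or decrease in BMI", the endpoint table in section 3 begins "1) maintain/reduce body mass index (BMI", and 9.4.1 says "Analyses will primarily test the hypothesis that intervention participants will have maintenance/reduction of BMI".

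**Visit.** The site description in 1.1 plans clinic visits at baseline, 5 and 12 months, and participant duration is 12 months. The Schedule of Activities (1.3) has a single follow-up column at 3 months, and 4.4 ends the study there. Section 3 says only "We are collecting data at baseline and post intervention". Sections 9.1 and 9.4.1 refer to follow-up without dating it.

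**Contrast.** Sections 1.1 (study description), 4.1, 5.5 and 6.1.1 all refer to a wait-list control group, and 4.1 and 5.5 say that allocation is random. Section 6.3 says this pilot does not randomise. Section 4.1 also names a comparison of virtual with earlier in-person delivery. Sections 9.1 and 9.4.1 test change from baseline to follow-up and name no control.

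**Model.** Section 9.4.1 adds: "Analyses will include the baseline level of each endpoint as a covariate and a continuous variable for time", and lists mixed models "to account for the repeated observations per participant".

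Section 9.4.2 (primary endpoint analysis) has a heading and no text, with no sign of redaction.

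**The concern.** A primary result needs one variable, one time point and one contrast. Here each has two incompatible versions in current text, and the section that should choose between them is blank.

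Two kinds of harm follow. First, some choices stay open after the data are in: BMI or BMI percentile and, if a control group is enrolled, a between-arm or a within-arm result. Second, the visit schedule and the allocation will be settled by how the study is run, but the protocol does not say which version is intended. Staff cannot follow it, and a reader cannot later tell whether it was followed.

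The contrast carries the most weight. Participants are selected for high BMI and for HbA1c in the prediabetes range (5.1). A pre-post change in such a group mixes any intervention effect with growth, time and regression to the mean. A randomised comparison does not.

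**Working it through.** The plan gives no sample size, power or alpha (9.2 has no text), so there is no figure to reproduce. The contradictions rest on the text. The arithmetic shows scale only.

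**1. Passages side by side**

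| Item | One version | Other version |
|---|---|---|
| Variable | BMI percentile: 1.1, 8.1, 9.1, 9.4.7 | BMI: 2.1, 3, 9.4.1 |
| Visit | 5 and 12 months, 12-month participation: 1.1 | 3 months only, end of study: 1.3, 4.4 |
| Contrast | Wait-list control: 1.1, 4.1, 5.5, 6.1.1 (randomised in 4.1, 5.5) | No randomisation: 6.3; baseline-to-follow-up change, no control named: 9.1, 9.4.1 |

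The 5- and 12-month follow-up in 2.2 belongs to the earlier cohort and is not used here. The site description in 1.1 is about the Zoom-delivered study, so that conflict is within the present trial.

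**2. How far BMI and percentile diverge.** Section 5.1 defines percentile for age and gender, so the reference moves as a participant ages. Assume a normal reference that rises by d SD per year (d = 0.05 to 0.20; assumed, not in the documents). If BMI is unchanged for t years, the percentile falls by p − Φ(z_p − d·t).

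| Starting percentile | 3 months (t = 0.25), d = 0.05 to 0.20 | 12 months (t = 1), d = 0.05 to 0.20 |
|---|---|---|
| 85th | 0.29 to 1.20 points | 1.20 to 5.15 points |
| 95th | 0.13 to 0.54 | 0.54 to 2.42 |
| 99th | 0.03 to 0.14 | 0.14 to 0.67 |

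Percentile is also compressed near 100. The same 0.10 SD fall is 2.45 points at the 85th, 1.12 at the 95th and 0.30 at the 99th.

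**3. The model in 9.4.1 (secondary).** Suppose there is a control arm and one follow-up visit.

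- *Baseline as covariate only.* Each participant has one response row. Time then varies only to the extent that visits move off schedule: later under 7.3 (rescheduling within a month) or earlier under 7.1 (assessments due within two weeks brought forward at discontinuation). If all visits fall at the same time, time cannot be separated from the intercept.
- *Baseline as both covariate and response, no arm-by-time term.* In the baseline rows the response equals the covariate, so the adjusted arm difference is 0. In the follow-up rows it is Δ, the baseline-adjusted difference. A single arm term averages the two. With complete follow-up this is (0 + Δ)/2 = 0.50Δ. Simulated data with 45 per arm gave −1.061 for Δ and −0.530 for the arm term, a ratio of 0.500.
- *The same with dropout.* If a fraction r returns, the follow-up rows carry weight about r/(1 + r). At the earlier cohort's 73% retention (2.2), 0.73/1.73 = 0.42. Simulation agreed: about 0.42.

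**4. Maintenance, if single-arm.** No margin is given. Suppose maintenance were claimed when the upper 95% limit of mean change lies below a margin of m SD of change, with true change 0 and 80% power. Then n ≈ ((1.96 + 0.84)/m)². That is 31.4 for m = 0.5 and 196 for m = 0.2. The non-central t gives 34 and 199 completers. Both margins are assumed.

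**The case against.** The strongest reply is that this is a pilot, that post-intervention follow-up most naturally means the 3-month visit, and that BMI and BMI percentile barely differ over 3 months. The last part stands: at the 95th to 99th percentile the divergence in step 2 is 0.03 to 0.54 points. The fourfold growth by 12 months reflects the assumed linear drift and is not evidence. But the pilot label does not remove the contradictions. Section 4.1 sets out to test effectiveness and 9.4.1 commits to hypothesis tests.

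Three stronger readings are tempting, and the documents do not support them.

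- A reader might multiply 2 variables, 3 visits and 2 contrasts and infer 12 primary analyses to choose from after the data are seen. No schedule in the text collects 3, 5 and 12 months, and allocation is fixed by conduct. With the 3-month schedule, 2 versions are open if single-arm (variable only) and 4 with a control (variable × between- or within-arm).
- A reader might take the halved arm coefficient as a built-in error of the plan. Section 9.4.1 says that baseline is a covariate. It does not say that baseline is also a response, nor that an arm-by-time term is left out. The result is a risk of one possible reading, and 0.50 needs complete follow-up.
- A reader might infer that the time variable could vary only through late visits. Section 7.1 can also move assessments earlier.

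**Conclusion.** The concern holds and must be fixed before analysis. Current text contradicts itself on the primary variable, visit and contrast, and 9.4.2 does not resolve it. This conclusion depends on no calculation.

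The contrast conflict is the most serious, since it decides whether the primary result can be attributed to the intervention. The visit conflict decides whether the Schedule of Activities lacks two planned visits. The variable conflict is small in size at 3 months and larger at 12, on assumed drifts. The documents give neither a planned sample size nor a baseline BMI distribution to refine this.

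The model ambiguity in 9.4.1 is secondary. Under the particular reading in step 3, the arm coefficient would be about half the adjusted difference with complete follow-up and about 0.42 of it at 73% retention.

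**What to change.** 1. **Variable.** Name one primary variable, in the same words, in 1.1, 2.1, 3, 8.1, 9.1, 9.4.1 and 9.4.2. Make the other secondary. Remove the copy of the primary hypothesis from 9.4.7, which is the subgroup section.
2. **Visit.** Reconcile 1.1, 1.3 and 4.4 to one schedule, and name one primary time point that the Schedule of Activities collects.
3. **Contrast.** Reconcile 1.1, 4.1, 5.5 and 6.1.1 with 6.3. Say whether virtual versus in-person delivery is analysed or only described. If randomisation stands, 6.3 must give the allocation method.
4. **Model, in 9.4.2.** With a control arm, make the primary estimate the between-arm difference at the primary visit, adjusted for baseline. With one follow-up visit, use either follow-up adjusted for baseline with no time term, or a repeated-measures model with baseline as a response and an arm-by-time term, but not both. If single-arm, report mean change with a 95% confidence interval and make no causal claim. Do not read a non-significant test as maintenance; claim maintenance only against a margin fixed in advance.

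**Cost.** A protocol amendment, which needs IRB approval (Statement of Compliance). If the 3-month schedule stands, no new measurement is needed, because 1.3 already collects height and weight at baseline and 3 months. If 5 and 12 months stand, those visits must be added to 1.3 and 4.4 must change. A small single-arm pilot may be unable to demonstrate maintenance (step 4).

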## 4 STUDY DESIGN

### 4.1 OVERALL DESIGN

We are now testing and evaluating outcomes of our refined intervention to reduce diabetes risk among ethnic minority pre-diabetic adolescents. We will further adapt the program for virtual delivery via a video conferencing platform to enhance access and attendance, and refine the text messaging platform to better support and engage teens.

We will identify at risk for diabetes adolescents and recruit adolescents (BMI in the overweight/obese range and HbA1c 5.7-6.4%) through electronic medical record data queries and referrals from clinical and community sites. Participation will be contingent on adolescent assent/parental consent (ages 13-17) or participant consent (ages 18 years or older). We will randomize pre-diabetic adolescents into intervention and wait list control (delayed intervention) groups to test intervention effectiveness. We will also evaluate the virtual and mHealth components of the intervention through usability testing and data analytics.

The intervention is 12 weekly 90-minute workshops based on feedback from our community advisory board and experts in peer led health education programs. The intervention will be offered via an online platform, Zoom, which is HIPAA compliant. We are testing the effectiveness of a virtual component versus our previous in-person workshop.

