## INCLUSION CRITERIA:

- Adolescents ages 13-19 years of age
- Residents of East or Central Harlem, members of an East or Central Harlem Institution, or patients seen in the Mount Sinai Health System. Membership in an East or Central Harlem institution includes the following: 1) attending a school in East or Central Harlem, 2) attending an after school or recreational activity in East or Central Harlem, or 3) receiving health care in East or Central Harlem. We will not ask participants for any identification for proof of address or membership in an East or Central Harlem institution. After informed consent is obtained for the adolescent to take part in the study, we will ask for the adolescent's full residential address. We will include those participants who live in supportive housing (such as shelters) and do not have plans to relocate from N.Y.C in the next year.
- Body mass index (BMI) percentile consistent with overweight/obesity (>85th percentile for age and gender based on Centers for Disease Control and Prevention definition).
- Hemoglobin A1c in prediabetes range (>5.7% or <6.5%)
- English speaking (resources available to us at this time limit inclusion of English speaking participants only). Note: only adolescents must be English speaking. Parental consent forms will be available in English and Spanish. The Spanish consent form will be submitted for IRB review with a letter of attestation from the translator after approval of the English consent form.
- Able to communicate verbally to participate in a group education class.
- Demographics:

(a) Gender: Males yes  no   
Females yes  no

(b) Age range: from 13 to 19  
(c) Racial and Ethnic Groups:

Caucasian	yes 	no 
Black	yes 	no 
Hispanic	yes 	no 
American Indian	yes 	no 
Alaskan Native	yes 	no 
Asian/Pacific Islander	yes 	no 
Other (specify) _____		

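### If BMI percentile is the primary outcome, its compression near 100 biases the before-after result toward maintenance or decrease

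*Combined protocol and SAP*

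**What the plan says.** Section 9.1 states the primary hypothesis as "We hypothesize that the TEEN HEED intervention will result in maintenance or decrease in BMI percentile", and sections 1.1, 8.1 and 9.4.7 repeat it. The reason given is that "We chose this outcome because weight loss is consistently shown as the most powerful and effective diabetes prevention strategy".

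Three other places use BMI without the percentile. Section 2.1 expects that "such an intervention will lead to maintenance or decrease in BMI", the endpoint table in section 3 lists BMI, and section 9.4.1 says "Analyses will primarily test the hypothesis that intervention participants will have maintenance/reduction of BMI".

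Section 5.1 requires a "Body mass index (BMI) percentile consistent with overweight/obesity", meaning above the 85th percentile for age and gender, and sets no upper limit. Sections 9.1 and 9.4.1 compare follow-up with baseline. On method, 9.4.1 says "Initial bivariate comparisons will use t tests to compare continuous endpoints", followed by adjusted models. Sections 9.2 (sample size) and 9.4.2 (primary analysis) have headings but no text. Maintenance is not defined and has no margin.

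**The concern.** A percentile cannot exceed 100, and it moves less and less per unit of BMI as it approaches 100. Entry is open-ended upward, so some participants may sit where a substantial gain or loss changes the percentile by a fraction of a point. Two things follow if percentile is the analysed variable. The mean change mostly reflects participants near the 85th percentile. And because the curve bends downward over the enrolled range, equal gains and losses in BMI z-score do not cancel: the loss moves the percentile further than the gain does. That tilts the mean toward the favourable answer.

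At stake is the direction of the main conclusion. A cohort with no average change, or a small average gain, could be reported as having maintained or reduced its weight status. With no margin for maintenance and no text in 9.4.2, nothing in the plan guards against this.

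**Working it through.** **Inputs from the plan.** Entry above the 85th percentile with no upper limit (5.1); comparison of follow-up with baseline (9.1, 9.4.1); t tests for continuous endpoints (9.4.1). The plan gives no sample size, significance level, SD or effect size, so there is no figure of its own to reproduce.

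**Assumptions, none from the plan.** Percentile = 100·Φ(z), where z is the BMI-for-age z-score. For the simulations: baseline uniform in percentile above the 85th (or 95th), z capped at 3, individual change normal on the z scale, paired t test at two-sided 0.05.

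**Step 1: compression.** Change in percentile = 100·[Φ(z ± 0.2) − Φ(z)].

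| Baseline | Gain of 0.2 z | Loss of 0.2 z |
|---|---|---|
| z = 1.1 (86th) | 90.32 − 86.43 = +3.89 | −4.84 |
| z = 1.645 (95th) | 96.75 − 95.00 = +1.75 | −2.42 |
| z = 2.0 | 98.61 − 97.72 = +0.88 (unrounded) | −1.32 |
| z = 2.5 | 99.65 − 99.38 = +0.27 | −0.45 |
| z = 3.0 | 99.93 − 99.87 = +0.07 (unrounded) | −0.12 |

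The slope of the curve relative to the 85th percentile is 0.44 at the 95th and 0.11 at the 99th. In every row the loss moves the percentile further than the equal gain.

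**Step 2: no true mean change.** With mean z change 0, SD 0.25 and n = 40 above the 85th, mean percentile change is about −0.56 points. The paired t test shows a significant decrease in about 11% of runs, against a nominal 2.5% in that tail. Varying n from 20 to 90 and the SD from 0.15 to 0.35 z gives 4% to 43% for a cohort above the 85th, and 5% to 65% for one above the 95th. The rate rises with n and with the SD.

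**Step 3: a true mean gain of 0.1 z (SD 0.25).** Probability of a significant increase:

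| n | On z, above 85th | On percentile, above 85th | On percentile, above 95th |
|---|---|---|---|
| 20 | 0.41 | 0.20 | 0.17 |
| 40 | 0.69 | 0.29 | 0.20 |
| 90 | 0.96 | 0.53 | 0.33 |

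**Step 4: a true mean loss of 0.1 z (SD 0.25, n = 40, above the 85th).** Power to show a decrease is about 0.85 on percentile and 0.69 on z.

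**Step 5: the sign can reverse.** Suppose 30% start at the 88th percentile and lose 0.2 z, and 70% start at the 99th and gain 0.2 z.
- Mean z change: 0.3 × (−0.2) + 0.7 × 0.2 = +0.08.
- Percentile change: −4.48 at the 88th and +0.42 at the 99th.
- Mean percentile change: 0.3 × (−4.48) + 0.7 × 0.42 = −1.05 points.

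The cohort gains on z and falls on percentile.

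**The case against.** The strongest reply is that percentile is not the settled outcome. The endpoint table and the only analysis text name BMI, which has no ceiling. That stands: the problem arises only if the conflict is resolved in favour of percentile, and the sections must be reconciled in any case. But four sections name percentile, so reconciling toward it is a real possibility.

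The second reply is that the trial enrols overweight as well as obese teens and gives no baseline distribution. This also stands. A reader might infer that the whole sample sits on the flat part of the curve, but step 1 shows percentile still responds at the 86th and 95th.

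A reader might also infer that the heaviest participants meet the hypothesis automatically. The plan contains no such rule: a move from 99.0 to 99.4 is still a rise, and it becomes maintenance only through rounding, a tolerance or a non-significant test, none of which is specified. Nor does the plan support saying that true loss goes undetected. Individual changes in severe obesity are tiny in points, but step 4 shows that power for a mean loss is not reduced.

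The use of age and gender norms for eligibility does not rule out BMI in kg/m² as the outcome over about 3 months, especially as 9.4.1 already adjusts for age, gender and baseline BMI.

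Two further limits apply. The false-decrease rates are for a before-after test; section 4.1 describes a randomised wait-list group and 6.3 says there is no randomisation. In a two-group comparison with similar baselines and similar spread of change, the downward drift would largely cancel, but the compression would remain. And section 6.3 calls this a pilot, which limits the consequence, although 4.1 speaks of testing effectiveness.

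**Conclusion.** The concern holds in a conditional form. If BMI percentile is analysed as sections 1.1, 8.1, 9.1 and 9.4.7 state, the before-after result is weighted toward participants near the 85th percentile and biased toward maintenance or decrease. With the central assumptions (n = 40, SD 0.25 z, baseline uniform above the 85th), the false-decrease rate is about four times nominal (11 / 2.5 = 4.4), and the chance of detecting a true mean gain of 0.1 z falls by more than half (0.69 to 0.29).

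These sizes rest on an assumed baseline distribution, SD and sample size, and the share of participants near the ceiling is unknown. The direction of the drift follows from the shape of the curve above the median and does not depend on those values. The point is worth correcting before analysis because the error favours the hypothesis and is cheap to avoid.

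**What to change.** In sections 1.1, 2.1, 3, 8.1, 9.1, 9.4.1, 9.4.2 and 9.4.7, name the same single primary variable, one that does not flatten at the top. One choice is change in BMI as a percentage of the age- and sex-specific 95th percentile; change in BMI in kg/m², adjusted for age, sex and baseline, is also acceptable. Keep BMI percentile for eligibility and description only.

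In 9.4.2, state the test and the confidence level. State also that maintenance is concluded only if the upper confidence limit for mean change lies below a margin fixed before analysis, and not from a non-significant test. Changing the scale without this step would still allow an imprecise gain to be called maintenance.

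The cost is protocol wording, one derived variable and agreement on a margin. Height and weight are already measured at baseline and 3 months (1.3), and age and sex are listed in 9.4.5, so no new measurement is needed. The percent-of-95th measure is less familiar to lay readers; the percentile can still be tabulated alongside it.
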